### **Statistical Analyses by Aim**

#### **Aim 1 (Primary Outcome): Show that EASE improves emotion regulation.**

First, to test the main effects of EASE on impaired ER (Hyp 1a) and maladaptive ER strategy use (Hyp 1b), we will employ linear mixed-effects models, with an auto-regressive error structure most appropriate to longitudinal data, allowing model intercepts and longitudinal trajectories to vary across subjects. Significant treatment by time interactions showing differences in linear rates of change in EDI Reactivity (Hyp 1a) and RSQ Involuntary and Voluntary Engagement scores (Hyp 1b) will be the effects of interest in these models. All mixed-effects models will control for potential demographic and medication confounds by including age, gender, IQ, and medication information as model covariates. This will be followed by modeling of growth trajectories between groups via HLM, also controlling for relevant potential confounds, using weekly data for Hyp 1a (EDI), and pre, mid, and post-treatment data for Hyp 1b (RSQ).

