Recruitment. This study will take place at: The University of Pittsburgh (Pitt.) in Pittsburgh, PA and Virginia Tech (VT) in Blacksburg, VA. Pitt Sample. [name] is associated with the Center for Excellence in Autism Research which has been running studies with verbal individuals with ASD for 30+ years. [name] recently completed two studies with adolescents (10-17 and 12-19) with ASD. In an assessment-focused study, 30 adolescents were recruited within less than 2 years. In an fMRI study, 26 adolescents with ASD were enrolled within 1 year. [name] also leads a study on the ASD specialized psychiatric inpatient unit at Western Psychiatric Institute and Clinic, where the reason for admission is typically emotional and behavioral dysregulation; this will be an ongoing source of recruitment (upon discharge). Finally, [name] has established collaborations and recruitment strategies in place with the Pittsburgh Autism Treatment Network and a high-volume outpatient clinical for ASD. VT Sample. In a recently completed RCT with adolescents with ASD, over a 24-month recruitment period, 36 potential participants were screened for eligibility (which was more stringent than current study), of whom 83% ( $n = 30$ ) met study criteria and were randomized. In two separate funded treatment trials currently underway, [name] is enrolling (on average) 2 adolescents and 2 adults per month. The clinic where this study will take place is well-recognized in the community, with a waiting list for treatment and registries carried over from prior studies. Additionally, [name] is a stakeholder and affiliate of the VT Center for Autism Research, a large-scale participant registry of children and adults with ASD interested in treatment research.

Eligibility determination and sample characterization will begin by phone, following verbal consent to screen. Phone screening will include a brief interview about the inclusion and exclusion criteria, including the 7-item EDI Reactivity Short Form. If participants pass the phone screen, they will complete an in-person informed consent/assent and assessment to confirm their ASD diagnosis and ensure that their Verbal IQ  $\geq$  80.

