### Primary Outcome (Emotion Regulation) Measures:

We have two measures of our primary outcome: (1) The EDI, which measures impaired ER, collected weekly parent report (short form), other reporter at pre-, post- and follow-up, and blind rater interview of the participant at pre-, post- and follow-up; and (2) The RSQ self- and parent report as a measure of ER strategies, collected at pre-, mid- and post-treatment, and 3-month follow-up.

Emotion Dysregulation Inventory (EDI; [name] et al., 2016). The EDI was developed to assess the full range of ER impairment observed in ASD. The item pool was created with feedback from parents of youth and young adults with ASD and input from a panel of experts in measure development and ER in ASD. Next, caregivers of 1,755 youth with ASD completed 66 candidate EDI items, and the final 30 were selected based on factor analysis and item response theory (IRT) analyses. The EDI has two scales: 1) *Reactivity*, characterized by intense, rapidly escalating, sustained and poorly regulated negative emotional reactions, and 2) *Dysphoria*, characterized by minimal positive affect and motivation, and the presence of nervousness and sadness. A 7-item Reactivity short form was developed via simulated computerized adaptive testing, which is correlated .98 with the full scale. Validity evidence was supported by expected group differences (higher scores in an ASD

psychiatric inpatient versus community sample), expected correlations with measures of related constructs, and demonstration of change sensitivity. Co-calibration with legacy measures demonstrated that the EDI provides substantially more information on individual variability in ER; Figure 7 shows these test information curves for the full EDI Reactivity scale, the 7-item EDI short form, the ABC-I (15 items), an emotion dysregulation index from the CBCL (Sampson et al., 2014), and CBCL Stress Problems Scale. In a sample of 432 youth with ASD with stable treatments, paired samples t-tests across a 4-week period yielded a very small effect size (-0.06), which will be helpful in judging the meaning of EDI effect sizes for EASE.

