## 1.J.a. STATISTICAL PLAN AND DATA ANALYSIS

### **Justification of sample size that is necessary to achieve the desired power**

We will enroll 80 subjects at two sites. Using small-scale pilot pre-post repeated measures data ( $n = 12$ ), we estimated the sample size to achieve the power of 0.80 for testing each hypothesis stated in the Aims 1 and 2 above from the EASE open trial. For the hypotheses to provide evidence that EASE has a differential treatment effect on ER, functional impairment, psychiatric symptoms, and problem behaviors (hypotheses 1a, 1b, 2a, 2b), Cohen's  $d$ , or standardized mean difference, ranged from small-to-medium effect size (0.41 for Anxiety) to very large (2.81 for CGI-I). The necessary sample size to detect the smallest effect size was computed as a total of 49 (per group), with a range of 4 to 28 per group for all other outcomes with larger effect sizes, and an average across measures of 17 per group. Our primary interest is in effects with at least moderate effect sizes, as they are likely to have the most real-world impact. As such, even if there was significant attrition, we should have ample power to detect the most meaningful outcomes for Aim 1 and Aim 2. To test the mediation effects (Exploratory Aim 4), we obtained the required sample size using the methodology proposed by Judd et al. (2001) and elaborated by Montoya & Hayes (2017). A necessary condition to detect mediation is that the change score for a mediator needs to be statistically significantly associated with the change score in dependent variable after controlling for the average level of the mediator. Using this framework, we found that the necessary total sample size to detect the mediation effect with power of .80 ranged from 43 to 86 (per group), where the effect size as a partial correlation in multiple linear regression ranged from large (0.44, path: Treatment  $\rightarrow$  CAMM Mindfulness  $\rightarrow$  RSQ Involuntary Disengagement) to medium (0.31, path: Treatment  $\rightarrow$  EDI reactivity  $\rightarrow$  Depression). The maximum sample size that we can feasibility ascertain for this project is 80, which gives us a chance to detect mediation processes that have large effects; accordingly, this aim is considered exploratory.

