**Intent to Treat Analyses and Approach to Missing Data.** Automated systems are in place via our online data collection (piloted during our open trial) to minimize occurrence of missing data. Nonetheless, intent-to-treat analyses of treatment effects will include all 80 individuals, regardless of attrition or infidelity to treatments. Both of our analytic approaches allow for missing data. ANOVA mixed models do not require that subjects be

excluded from the analyses because of a single missing data point. Multilevel growth models can also make an efficient estimation by utilizing all the available data, and further, the estimates are valid (i.e., asymptotically unbiased) when missingness occurs at random (MAR) (Little & Schenker, 1995). Even when MAR is not satisfied, the robustness of the results is maximized when all available data are used in the analysis (Schafer, 1997). In order to accommodate the case of missing ‘not at random,’ we plan to conduct a sensitivity analysis to see how much our inferences would be altered using a pattern-mixture model (Hedeker & Gibbons, 2006).

**Controlling Experimental-Wise Type I Error Rates.** The conduct of multiple tests of statistical inference can artificially increase Type I error rates. Several approaches will be used to control the experimental-wise error rate in this trial. First, analyses conducted to test the hypotheses of Aims 1 through 3 will be given priority over exploratory analyses conducted as part of Aim 4. Since these hypotheses about efficacy and durability of the proposed EASE program on ER and functional impairment have confirmatory nature from our prior studies and are the main hypotheses in this clinical trial, we will employ Hochberg’s correction (Hochberg, 1988) to control the experimental-wise error rate by adjusting p-values for multiple hypothesis tests in order to rigorously examine the treatment efficacy and durability. Second, in order to address the hypotheses in Aim 4, outcome measures will initially be aggregated into four multivariate composite domains (i.e., ER, functional impairment, psychiatric symptoms, and problem behaviors) based on internal consistency analyses and previous studies, which will reduce the number of hypothesis tests initially conducted. Then, exploratory analyses will be conducted for individual measures within these composite domains only if the overall multivariate composite demonstrates a significant mediation effect.

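### The Aim 1 slope models state no adjustment for baseline EDI or RSQ and no common baseline mean, so the primary test may be less precise than the data allow (efficiency, not bias)

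*Combined protocol and SAP*

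**What the plan says.** The Aim 1 text specifies linear mixed models with autoregressive errors, "allowing model intercepts and longitudinal trajectories to vary across subjects". The test is on "Significant treatment by time interactions showing differences in linear rates of change in EDI Reactivity (Hyp 1a" and on the matching RSQ slopes for Hyp 1b. Confounding is handled "by including age, gender, IQ, and medication information as model covariates". A follow-on HLM is fitted "using weekly data for Hyp 1a (EDI), and pre, mid, and post-treatment data for Hyp 1b (RSQ", so the pre-treatment RSQ is one of the modelled outcome points.

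Both outcomes are available before treatment. In section 1.I.d, "Phone screening will include a brief interview about the inclusion and exclusion criteria, including the 7-item EDI Reactivity Short Form". The outcome-measures section describes "The RSQ self- and parent report as a measure of ER strategies, collected at pre-, mid- and post-treatment, and 3-month follow-up". Randomisation follows confirmed eligibility, and the participant is then told the assignment. The plan does not say whether the pre-treatment battery is completed before that disclosure.

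Nowhere does the plan list the baseline outcome score as a covariate, state a common baseline mean, or say whether a treatment main effect is in the model.

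**The concern.** With a treatment main effect in the model, each arm gets its own fitted starting level. Randomisation makes the true baseline difference zero, so estimating it spends information. Because the estimated starting level and slope are correlated within an arm, a chance baseline imbalance also adds noise to the slope contrast. Holding the arms equal at baseline removes that noise and keeps every time point and the slope test.

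Precision is scarce here. Enrolment is capped at 80, with 60 expected after 25% attrition, and p-values across Aims 1 to 3 are Hochberg-adjusted "to control the experimental-wise error rate by adjusting p-values for multiple hypothesis tests". Power not taken from the analysis cannot be regained by recruiting.

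**Working it through.** **Inputs from the plan.** Equal allocation; 80 enrolled gives 40 per arm and 60 remaining gives 30 per arm. Random intercept, random slope, autoregressive errors. EDI weekly (taken as weeks 0 to 16); RSQ at weeks 0, 8 and 16. Pilot EDI change SD 0.67.

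**Assumed, because the plan is silent.** Two-sided 0.05; a true difference growing linearly to 0.5 baseline SD at week 16; complete data; covariates ignored; all correlations and variance components.

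**The plan's own figure.** The plan states "we estimated the sample size to achieve the power of 0.80 for testing each hypothesis" and gives 49 per group for d = 0.41. A single-arm paired t-test reproduces it: power is 0.794 at n = 48 and 0.803 at n = 49. A two-arm comparison needs 2(1.96 + 0.842)²/0.41² = 93.4, or 94 per group. That is a separate matter. Here it means that the plan has no power figure for the between-arm slope test.

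**Effect of a common baseline mean.** Scale time to 0 at baseline and 1 at week 16. Let C = (X′V⁻¹X)⁻¹ for one participant's intercept and slope.

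- Free arm intercepts: Var_free = 2·C_slope/n.
- Common baseline mean: Var_common = Var_free·(1 − r²), where r is the correlation of the estimated intercept and slope.
- Power = Φ(0.5/√Var − 1.96).

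Since r² is never negative, the constraint cannot increase this variance.

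**RSQ, three waves, compound symmetry.** Var_free = 4(1 − ρ)/n and r² = (1 − ρ)/{2[ρ + (5/6)(1 − ρ)]}. At ρ = 0.5 and n = 40:

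- Free: variance 0.05, SE 0.2236, power Φ(2.236 − 1.96) = 0.609.
- Common: r² = 0.5/1.833 = 0.273, variance 0.0364, SE 0.1907, power Φ(2.622 − 1.96) = 0.746.

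| ρ | Variance cut | Power, 40 per arm | Power, 30 per arm |
|---|---|---|---|
| 0.5 | 27% | 0.609 → 0.746 | 0.491 → 0.622 |
| 0.54 | 25% | 0.645 → 0.767 | 0.524 → 0.644 |
| 0.7 | 16% | 0.823 → 0.882 | 0.705 → 0.778 |
| 0.78 | 11% | 0.921 → 0.948 | 0.831 → 0.873 |

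The values 0.54 and 0.78 are borrowed from EDI through ρ = 1 − 0.67²/(2·SD²). SD = 1 gives 0.78. SD = 0.70, a standard normal cut at T 45, gives 0.54. Both SDs are assumptions.

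**The plan's covariance structure, 40 per arm.** Baseline variance 1; intercept variance 0.4 to 0.8 in steps of 0.1, residual the remainder; slope variance 0.04, 0.16, 0.36; intercept-slope correlation −0.3, 0, +0.3; weekly AR(1) 0, 0.3, 0.6. This makes 135 combinations.

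| Intercept-slope correlation | Weekly EDI gain in points, median (range) | RSQ gain in points, median (range) |
|---|---|---|
| −0.3 | 7.0 (0.0 to 18.9) | 13.4 (3.4 to 19.5) |
| 0 | 3.1 (0.0 to 15.1) | 8.5 (2.2 to 16.5) |
| +0.3 | 0.7 (0.0 to 12.4) | 4.7 (0.1 to 14.1) |
| All | 3.2 (0.0 to 18.9) | 8.0 (0.1 to 19.5) |

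The median depends on the grid. Dropping intercept variance 0.4 gives 1.7 for EDI and 7.1 for RSQ; another broad grid gave about 3 and 6.

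**Modelling only post-baseline scores.** With baseline and baseline-by-time as covariates but the treatment main effect kept, the RSQ slope rests on weeks 8 and 16 alone: Var = 16(1 − ρ)/n. At ρ = 0.5 and n = 40 this is 0.2, SE 0.447, power Φ(1.118 − 1.96) = 0.20. At ρ = 0.78 it is 0.39, against 0.92 for the free-intercept model. With the main effect at time 0 also omitted, power returns to 0.746 at ρ = 0.5, the same as the constrained model.

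**Validity.** In 20,000 simulated trials at 40 per arm, type I error with free and common baselines was 0.050 and 0.051 for EDI, and 0.051 and 0.052 for RSQ.

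**The case against.** Keeping baseline as a response in a random-intercept growth model is standard and valid, and the simulated type I error bears this out. That stands: nothing here is a bias under randomisation.

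A reader might infer that the plan fits separate arm intercepts. It does not say so. The usual reading includes the main effect, but the supportable statement is that the plan states neither baseline adjustment nor a common mean.

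A reader might also infer a typical loss of 3 to 14 points. That range belongs to RSQ under compound symmetry, which the plan does not specify. Under its random slopes the gain can nearly vanish: for RSQ with intercept variance 0.8, slope variance 0.36, residual 0.2 and correlation +0.2, power moves only from 0.727 to 0.732. The documents contain nothing that picks out a typical value.

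At the pilot RSQ effect (d = 2.67) power would be close to 1 and nothing would be lost. That figure is uncontrolled pre-post change in one arm, so it does not size a contrast with an active control.

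Larger gains appear if the full benefit is reached by week 8 and then held. Part of that is misfit of a straight line, a different issue, and the plan gives no basis for assuming that shape.

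Finally, the constraint is justified only for scores given before the arm is known, and the plan leaves that order open. This limits the fix but does not defeat it.

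**Conclusion.** The point holds as a cheap improvement. The Aim 1 models state no use of the baseline score beyond treating it as an outcome point, and on the ordinary reading they give up some precision on the primary question. The size cannot be fixed from the documents. At 0.5 SD, two-sided 0.05 and 40 per arm it runs from about 0 to 19 power points under the plan's own model. It is larger when high starters tend to decline faster (negative intercept-slope correlation) and can be near 0 when that correlation is positive. No combination examined showed a loss from the common-baseline model. The result assumes linear divergence, complete data and baseline scores unaffected by knowledge of the arm.

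**What to change.** In the Aim 1 mixed model and the HLM, for EDI Reactivity and RSQ:

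- Keep the baseline score as a response, fit time and treatment by time, and omit the treatment main effect at time 0, so that the arms share one baseline mean. Keep the listed covariates and the slope test.
- If post-baseline scores are modelled instead, with baseline and baseline-by-time as covariates, state that the treatment main effect at time 0 is omitted there too.
- Apply the constraint only to scores completed before the arm is disclosed, and state that order in the plan.
- If the pre-treatment EDI came after disclosure, use the phone-screen EDI short form as the baseline covariate with its time interaction, again without the arm main effect at time 0. The plan should say who answers that form at screening.
- If the RSQ baseline came after disclosure, keep the unconstrained model for RSQ, since no screening RSQ is described.

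The cost is SAP wording and one model term, with no new data, visits or staff. The one downside is the dependence on scores taken before disclosure.

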|---------------------------|------------------------------|----------|-------------------------------|----------|----------|----------|
| Functional Impairment     | CGI-Improvement              | 12       | -1.75 (.62)*                  | 2.81     | -9.75    | <.001    |
| Impaired ER               | EDI-Reactivity theta score   | 11       | -.49 (.67)                    | .73      | -2.40    | .037     |
| Maladaptive ER strategies | RSQ – Involuntary engagement | 11       | -11.46 (4.30)                 | 2.67     | -8.84    | <.001    |
| Depression                | PROMIS-Depression            | 11       | -7.27 (8.26)                  | .88      | -2.92    | .015     |
| Problem Behavior          | ABC-Irritability             | 11       | -5.73 (7.25)                  | .79      | -2.62    | .026     |
| Anxiety                   | PROMIS-Anxiety               | 11       | -4.46 (10.85)                 | .41      | -0.98    | .203     |

**Note.** \*For CGI-I, value represents mean change from 4, which equals no improvement; Parent report data shown

**Figure 3.** Illustrative examples of group mean change in key measures from baseline to post-treatment

Preliminary Efficacy evidence in young adults. Some of EASE’s content was informed by [name] & [name] (2017)’s ER-focused MBI open pilot that involved nine young adults with ASD age 18-25 who reported impaired ER (no cutoff on ER impairment was used). The baseline CGI-Severity scores covered the same range as the adolescent sample, though the adult sample was slightly less impaired, with a mean baseline severity (CGI-S) of 3.67 (*SD* = .71). The CGI-Improvement scores were similar to the EASE adolescent sample (2-3; *M*= 2.67; *SD*= .50). Treatment satisfaction was acceptable (*M*= 8.13; scale 1-10). In addition, seven of the nine participants had reliable improvement in impulse control, access to ER strategies, or emotional acceptance as measured on the Difficulty in Emotion Regulation Scale (Gratz & Roemer, 2004). While these results are promising, they are limited by the absence of a control group and lack of a required threshold for ER impairment to be enrolled in the study.

**Figure 4.** Individual and Mean Changes in DERS subscales

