### **Aim 1 (Primary Outcome): Show that EASE improves emotion regulation.**

- ❑ H1a: Participants in the EASE group will demonstrate a steeper decline in ER impairment, relative to the ACC group.
- ❑ H1b: Participants in the EASE group will demonstrate less reliance on maladaptive ER strategies, relative to the ACC group.

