### **Aim 3 (Durability): Examine the trajectory of change including the degree to which effects are sustained after treatment completion.**

- ❑ H3a: Participants in the EASE group will maintain significantly greater gains in ER ability, functioning, and reduced psychiatric symptoms, and at 3-months post-treatment follow-up compared to ACC group.

- ❑ H3b: ER impairment will not return to pre-treatment levels three months after treatment completion.

[figure not shown]

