**Response to Stress Questionnaire, Social Stress Version** (RSQ; Connor-Smith et al., 2000) is a 57-item self- and parent-report questionnaire of ER strategies. The RSQ asks the respondent to identify social stressors that they have experienced and then rate the questions related to these specific stressors, thereby making it more concrete and relevant to the lives of adolescents young adults with ASD. The RSQ has been shown to be valid and reliable in ASD samples ([name] et al., 2014; Khor et al., 2014). The RSQ will be used to explore the change in reliance upon maladaptive strategies (i.e., involuntary engagement and involuntary disengagement).

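### The Hypothesis 1b analysis tests RSQ Voluntary Engagement, which the protocol does not define as maladaptive, and omits Involuntary Disengagement, which it does

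*Combined protocol and SAP*

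**What the plan says.** In section 1H, Aim 1, Hypothesis 1b predicts that the EASE group "will demonstrate less reliance on maladaptive ER strategies, relative to the ACC group".

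The section on primary outcome measures gives the RSQ primary status: "We have two measures of our primary outcome", the EDI being one and the RSQ the other. The RSQ is "collected at pre-, mid- and post-treatment, and 3-month follow-up". The paragraph describing the RSQ says it will be used to look at change in "reliance upon maladaptive strategies (i.e., involuntary engagement and involuntary disengagement").

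Under Statistical Analyses by Aim, the Aim 1 text says the mixed models test "maladaptive ER strategy use (Hyp 1b"). It then says of the treatment-by-time effects that "RSQ Involuntary and Voluntary Engagement scores (Hyp 1b) will be the effects of interest in these models". The growth model that follows refers to the RSQ for Hypothesis 1b but names no scale.

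**The concern.** The analysis text states the right construct and then lists scores that do not match it. A statistician who follows it literally will fit a model to Voluntary Engagement and report it as a Hypothesis 1b effect. The hypothesis is about less maladaptive strategy use and the protocol does not class Voluntary Engagement as maladaptive, so neither a rise nor a fall on that scale can be read against it. Involuntary Disengagement, half of the definition, would have no named primary test.

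This is the score definition for a primary hypothesis. While the two sections disagree, either could be cited to justify the second score once results are known. The multiplicity paragraph applies Hochberg's correction to Aims 1 to 3 without listing the tests, so it does not settle which RSQ scores count.

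The gap can also reach Aim 3. Hypothesis 3a says the EASE group will "maintain significantly greater gains in ER ability", the RSQ is collected at follow-up, and the Aim 3 analysis names no RSQ scale.

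**Working it through.** No figure in the plan bears on the mismatch itself, so the check is a comparison of every place that names an RSQ scale.

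| Place | Role of the RSQ there | Involuntary Engagement | Involuntary Disengagement | Voluntary Engagement |
|---|---|---|---|---|
| Primary outcome measures, RSQ paragraph | Defines maladaptive strategies | Yes | Yes | No |
| Aim 1 analysis | Scores tested for Hypothesis 1b | Yes | No | Yes |
| Section 1.F, table of preliminary effect sizes | Pilot effect under maladaptive strategies | Yes | No | No |
| Section 1.J.a, sample size | Outcome of an Aim 4 mediation path | No | Yes | No |

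1. Definition = {Involuntary Engagement, Involuntary Disengagement}. Analysis = {Involuntary Engagement, Voluntary Engagement}. They have 1 scale in common and name 3 between them.
2. So 1 of the 2 analysed scores is outside the definition, and 1 of the 2 defining scales is not analysed by name.
3. Voluntary Engagement appears only in the Aim 1 analysis, without a direction or rationale.
4. A looser reading does not help. If the word Involuntary in the analysis sentence were taken to cover both involuntary scales, Voluntary Engagement would still be outside the definition and Involuntary Disengagement would still not be named.
5. The pilot table does not show which second score was meant. Its only RSQ row is "RSQ – Involuntary engagement", with n = 11 and mean change -11.46 (SD 4.30). That row is internally consistent: 11.46 / 4.30 = 2.665, against the reported d of 2.67; and 2.665 × √11 = 8.84, against the reported |t| of 8.84. But it concerns the one scale not in dispute. Neither disputed scale has a pilot pre-post effect, so power for either cannot be worked out from the document.

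**The case against.** The strongest reply is that this is a slip of wording. The RSQ paragraph states the maladaptive set in advance, and the sample size section uses Involuntary Disengagement as the outcome of a mediation path (partial correlation 0.44). Nothing outside the one analysis sentence supports Voluntary Engagement. The same sentence block still names the construct as maladaptive strategy use, so a Voluntary Engagement result could not plainly be claimed as support for Hypothesis 1b. Post-hoc selection is possible, not shown.

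A slip is indeed the likelier explanation. But the mediation path belongs to exploratory Aim 4 and cannot repair the primary analysis; it supports the proposed correction. The faulty sentence is the only one that specifies the scores.

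A deliberate choice cannot be fully excluded either: section 1.F discusses adaptive and maladaptive strategies together, and the RSQ paragraph speaks only of exploring change. That does not downgrade the RSQ, which the document lists as a primary measure and places under the Aim 1 primary hypotheses. If Voluntary Engagement was intended, it needs its own rationale and direction.

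Two further points have some force. The RSQ is completed by self and parent, and the Aim 1 analysis names no reporter, so two scales and two reporters leave 2 × 2 = 4 possible tests even after the scales are corrected. That is a real but separate gap. The Aim 3 text names no scale for any measure, so its silence on the RSQ is not caused by this error. The link to Aim 3 is secondary, and the conclusion does not depend on it.

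**Conclusion.** The Hypothesis 1b analysis is wrong as written and must be corrected. It names one score outside the protocol's own definition of maladaptive strategies and leaves one of the two defining scales without a named test. This affects one of the two primary outcome measures.

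The conclusion rests only on the document's wording: the RSQ paragraph gives a closed definition, and the Aim 1 analysis is the only text that names the Hypothesis 1b scores. It needs no view of what the RSQ scales ought to measure. Involuntary Engagement is consistent throughout, and Hypothesis 1a is not affected.

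**What to change.** Amend the Aim 1 analysis so that the Hypothesis 1b scores are RSQ Involuntary Engagement and RSQ Involuntary Disengagement, each with a decrease favouring EASE. Use the same scores in the mixed model and the growth model, and in Aim 3 wherever the RSQ is used there. If the sponsor wants Voluntary Engagement, report it outside Hypothesis 1b as secondary or exploratory, with its expected direction given in advance.

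Make the change before any outcome data are examined by arm. That is the useful milestone because the Randomization paragraph has assignments communicated to the principal investigators, so there is no later unblinding of the team to work from.

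The cost is one sentence in the analysis plan. No new data are needed, because the same questionnaire is already given. The reporter for the Hypothesis 1b scores could usefully be named in the same amendment.
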